8.1.2.1. Prespecified Criteria for (Suspected) COVID-19 (Adolescents)

The criteria for (suspected) COVID-19 (ie, the triggers to start procedures explained in Section 8.1.2) are prespecified as follows:

Positive RT-PCR result for SARS-CoV-2 for the participant, through a private or public laboratory independent of the study, whether symptomatic or asymptomatic

OR

A positive RT-PCR result for SARS-CoV-2 for a parent/caregiver, or any other close relative/contact of the participant, through a private or public laboratory independent of the study, whether symptomatic or asymptomatic

OR

New onset or worsening of any 1 of these symptoms, which lasts for at least 24 hours, not otherwise explained by an alternative diagnosis and in the presence of a suspected exposure:

^a long-term sequelae of COVID-19 will not be followed until their resolution

- Fever ($\geq 38.0^{\circ}\text{C}$ or $\geq 100.4^{\circ}\text{F}$) or chills
- Pulse oximetry value $\leq 95\%$, which is a decrease from baseline
- Tachycardia (according to age)
- Cough
- Nasal congestion or runny nose (rhinorrhea)
- Shortness of breath, difficulty breathing, or wheezing
- Diarrhea
- Vomiting
- Lethargy/tiredness/decreased activity
- Poor appetite or poor feeding
- Mood behaviors (frequently crying, irritability)
- Tachypnea (according to age)
- Bluish lips or face
- Red or bruised looking feet or toes
- New loss of taste or smell
- Muscle or body aches
- Neurologic symptoms (numbness, difficulty forming or understanding speech)
- Symptoms of blood clots: pain/cramping, swelling or redness in the legs/calves
- Other nonspecific symptoms such as: rash, bloodshot eyes or eye irritation/drainage, sore throat, stomachache, headache
- Clinical suspicion/judgement by investigator of symptoms suggestive of COVID-19, including MIS-C

As several of the prespecified criteria for suspected COVID-19 overlap with vaccine-related reactogenicity, investigators' clinical judgement is required to exclude vaccine-related events.

8.1.3. Procedures for Adolescents Whose Close Relative/Contact Has Suspected or Confirmed COVID-19

Testing for SARS-CoV-2 should be performed for all adolescents, regardless of whether there are signs of infection in the adolescent if their parent/caregiver or close relative/contact from the same household has suspected or confirmed COVID-19, refer to the procedures in Section [8.1.2](#).

Testing of asymptomatic and symptomatic adolescents should be performed according to the procedures in Section [8.1.2](#), within 48 hours after becoming aware of a positive test from the parent/caregiver or the close relative/contact.

For adolescents presenting with signs of infection suggestive of COVID-19 (see Section [8.1.2.1](#)), or with a positive SARS-CoV-2 test, refer to the procedures in Section [8.1.2](#).

8.1.4. Symptomatic SARS-CoV-2 Infection

Identification and local molecular confirmation of SARS-CoV-2 infection and symptomatic COVID-19 will be performed throughout the study as described in Section 8.1.2 and 8.1.3. The PRO to evaluate exploratory vaccine efficacy parameters will be the SIC.

Molecular confirmation of SARS-CoV-2 infection will be performed for the exploratory analysis of the case definition. The severity of all COVID-19 cases will be assessed using the case definitions in Section 10.9.

8.1.5. Asymptomatic SARS-CoV-2 Infection

A non-S protein ELISA (eg, SARS-CoV-2 N-ELISA) or SARS-CoV-2 immunoglobulin assay will be performed to identify cases of asymptomatic SARS-CoV-2 infection (see also Table 3). This assay will be performed at the timepoints specified in the SoA (Section 1.3).

Any asymptomatic participant with a positive molecular test result for SARS-CoV-2, regardless of where the testing was performed (under the auspices of the study or through a private or public laboratory independent of the study) will be considered. The positive molecular test result will need to be captured in the eCRF.

8.2. Safety Assessments

Details regarding the IDMC are provided in Section 10.3.6. The IDMC responsibilities, authorities, and procedures will be documented in the IDMC Charter.

Adverse events will be reported and followed by the investigator as specified in Section 8.3 and Section 10.4.

Any clinically relevant changes occurring during the study must be recorded on the AE section of the eCRF.

Any clinically significant abnormalities persisting at the end of the study/early withdrawal will be followed by the investigator until resolution or until a clinically stable condition is reached.

The study will include the following evaluations of safety and reactogenicity according to the time points provided in the Schedule of Activities (Section 1.3).

8.2.1. Physical Examinations

A history-directed physical examination, including length/height, body weight, will be assessed at screening. To obtain the actual body weight, participants must be weighed lightly clothed. The height should be measured without footwear.

At all other visits, an abbreviated, symptom-directed examination might be performed by the investigator based on any clinically relevant issues or symptoms, and medical history. Symptom-directed physical examination may be repeated if deemed necessary by the investigator.

Physical examinations will be performed by the investigator or designated qualified person. Any clinically relevant abnormalities or changes in severity observed during the review of body systems should be documented in the eCRF.

8.2.2. Vital Signs

Body temperature (in accordance with the local standard of care for adolescents), pulse/heart rate, preferably supine systolic and diastolic blood pressure, respiratory rate, and blood oxygen saturation will be assessed.

Pulse/heart rate measurements will be assessed with a completely automated device. Manual techniques will be used only if an automated device is not available. Pulse/heart rate measurements should be preceded by at least 5 minutes of rest (if feasible) in a quiet setting without distractions (eg, television, cell phones). Assessment of vital signs is recommended prior to blood sampling.

Participants will utilize a reactogenicity diary in the eCOA to record body temperature, preferably orally, measurements post-vaccination from the time of vaccination until 7 days after each vaccination.

Participants with (suspected) COVID-19 should measure blood oxygen saturation 3 times a day and body temperature daily (the highest temperature in the last 24 hours each day) and record it in the eCOA for the duration of follow-up of COVID-19 episodes (as defined in Section 8.1.2).

8.2.3. Pregnancy Testing

A urine pregnancy test for participants of childbearing potential will be performed at screening and before each vaccination.

Additional pregnancy tests may be performed, as determined necessary by the investigator or required by local regulation, to establish the absence of pregnancy at any time during the participation in the study.

For a participant who becomes pregnant, this information will be shared with the study participant's legal guardian as required or permitted by local regulations.

8.2.4. Hematology Clinical Laboratory Assessments

8.2.4.1. Thrombosis With Thrombocytopenia Syndrome

In case of a thrombotic event or TTS, every effort should be made to collect local hospital/laboratory test results obtained by the treating physician to allow rapid diagnosis and treatment. This information should be reported through the TTS AESI form (see Section 10.12) electronically per instructions in the eCRF completion guidelines. In addition, every effort should be made to collect blood samples from the participant for a platelet count (local laboratory or substitute for local laboratory) and other applicable testing (central laboratory) (see the Schedule of Activities in Section 1.3.4.1 and Section 10.2). The investigator will review the laboratory test results to assist the investigation of the AESI.

See Section 8.3.6.1 for details on laboratory test details to be reported for an AE of thrombocytopenia.

8.2.4.2. Multisystem Inflammatory Syndrome in Children

In case of MIS-C, every effort should be made to collect local hospital/laboratory test results obtained by the treating physician to allow rapid diagnosis and treatment. This information should be reported through the MIS-C AESI form (see Section 10.13) electronically per instructions in the eCRF completion guidelines. In addition, every effort should be made to collect and other applicable testing (central laboratory) (see the Schedule of Activities in Section 1.3.4.2 and Section 10.2). The investigator will review the laboratory test results to assist the investigation of the AESI.

See Section 8.3.6.2 for details on laboratory test details to be reported for an AE of MIS-C.

8.3. Adverse Events, Serious Adverse Events, Medically-attended Adverse Events, Adverse Events of Special Interest, and Other Safety Reporting

Timely, accurate, and complete reporting and analysis of safety information, including AEs, SAEs, MAAEs, AESIs, and product quality complaint (PQC), from clinical studies are crucial for the protection of participants, investigators, and the sponsor, and are mandated by regulatory agencies worldwide. The sponsor has established Standard Operating Procedures in conformity with regulatory requirements worldwide to ensure appropriate reporting of safety information; all clinical studies conducted by the sponsor or its affiliates will be conducted in accordance with those procedures.

Adverse events will be reported by the participant (or, when appropriate, by a caregiver, surrogate, or the participant's legally acceptable representative) for the duration of the study.

Further details on AEs, SAEs, MAAEs, AESIs, and PQC can be found in Section 10.4.

8.3.1. Time Period and Frequency for Collecting Adverse Event, Medically-attended Adverse Event, Adverse Event of Special Interest, and Serious Adverse Event Information

All Adverse Events

All AEs and special reporting situations, whether serious or non-serious, that are related to study procedures or that are related to non-investigational sponsor products will be reported for all participants from the time a signed and dated ICF is obtained until the end of the study/early withdrawal.

Clinically relevant medical events not meeting the above criteria and occurring between signing of the ICF and moment of first vaccination will be collected on the Medical History eCRF page as pre-existing conditions.

Solicited AEs, collected through a reactogenicity diary as part of the eCOA, will be recorded for each vaccination from the time of vaccination until 7 days post-vaccination.

All other unsolicited AEs and special reporting situations, whether serious or non-serious, will be reported for each vaccination from the time of vaccination until 28 days post-vaccination. Unsolicited AEs with the onset date outside the timeframe defined above (>28 days after previous study vaccination), which are ongoing on the day of the subsequent vaccination, should be recorded as such.

All SAEs and AEs leading to discontinuation from the study/vaccination (regardless of the causal relationship) are to be reported for all participants from the moment of first vaccination until completion of the participant's last study-related procedure, which may include contact for safety follow-up. The sponsor will evaluate any safety information that is spontaneously reported by an investigator beyond the time frame specified in the protocol.

MAAEs are defined as AEs with medically-attended visits including hospital, emergency department, urgent care clinic, or other visits to or from medical personnel for any reason. Routine study visits will not be considered medically-attended visits. New onset of chronic diseases will be collected as part of the MAAEs. MAAEs are to be reported for all participants from the first vaccination until 6 months after each vaccination, except for MAAEs leading to study discontinuation which are to be reported during the entire study.

To enable prompt response to a situation that could trigger pausing rules, the investigator should notify the sponsor's medical monitor or designee (AND fax or email the SAE form to Global Medical Safety Operations, if applicable), immediately and no later than 24 hours after becoming aware of any related AE of Grade 3 or above AND update the eCRF with relevant information on the same day the AE information is collected as described in Section [6.8](#).

All AEs will be followed until resolution or until clinically stable.

Adverse Events of Special Interest

From the time of local approval of protocol Amendment 1 onwards, TTS (Section [8.3.6.1](#)) and MIS-C (Section [8.3.6.2](#)) are considered to be AESIs. Suspected AESIs (thrombotic events and thrombocytopenia [defined as platelet count below 150,000/ μ L] [[BC 2021](#)], and MIS-C) will be recorded from the moment of vaccination until the end of the study/early withdrawal. An AESI Adjudication Committee with appropriate expertise will be established to evaluate each suspected AESI and determine cases of TTS (Section [8.3.6](#)).

Serious Adverse Events

All SAEs, as well as PQC, occurring during the study must be reported to the appropriate sponsor contact person by study-site personnel within 24 hours of their knowledge of the event.

Serious adverse events, including those spontaneously reported to the investigator, must be reported using an SAE form. The sponsor will evaluate any safety information that is spontaneously reported by an investigator beyond the time frame specified in the protocol.

Information regarding SAEs will be transmitted to the sponsor using the Serious Adverse Event Form and Safety Report Form of the eCRF, which must be completed and reviewed by a physician

from the study site, and transmitted to the sponsor within 24 hours. The initial and follow-up reports of an SAE should be transmitted electronically or by facsimile (fax). Telephone reporting should be the exception and the reporter should be asked to complete the appropriate form(s) first.

Signs and symptoms of MIS-C will be monitored and reported as SAE in adolescents with (suspected) COVID-19 as confirmed by a positive molecular test result for SARS-CoV-2, and in adolescents whose parents/caregivers or close relatives/contacts have a prior (within 4-weeks) or current suspected or confirmed COVID-19. Further details on case definition and reporting of MIS-C in adolescents can be found in Section 10.8.

8.3.2. Method of Detecting Adverse Events, Medically-attended Adverse Events, Adverse Events of Special Interest, and Serious Adverse Events

Care will be taken not to introduce bias when detecting AEs, MAAEs, suspected AESIs, or SAEs. Open-ended and nonleading verbal questioning of the participant is the preferred method to inquire about AE occurrence.

Study-site personnel, as well as parents and caregivers, should be instructed how to interpret signs and symptoms (eg, crying and pain) in their individual child. They will be instructed to report both specific and nonspecific symptoms (including vomiting, diarrhea, sleepiness, variation in the intensity and pattern of crying, etc). These nonspecific symptoms may be the only manifestations of some adverse reaction observed in adolescents. Care should be taken that the clinical presentation of adverse reactions is not misinterpreted as the manifestation of a pre-existing or unrelated condition.

Moreover, symptoms that are dependent on participant communication ability (eg, nausea, pain, mood alterations) in younger or mentally-disabled adolescents could potentially be at risk for under- or mis-reporting.]

These events may or may not have been noted in the participant's reactogenicity diary.

Solicited Adverse Events

Solicited AEs are used to assess the reactogenicity of the study vaccine and are predefined local (at the injection site) and systemic events for which the participant is specifically questioned, and which are noted by participants in their reactogenicity diary.

After each vaccination, adolescents will remain under observation at the study site for at least 30 minutes (or longer if required by institutional/local practice) for the presence of any acute reactions and solicited events.

In addition, participants will record solicited signs and symptoms in a reactogenicity diary for 7 days post-vaccination. All participants will be provided with a reactogenicity diary and instructions on how to complete the reactogenicity diary (see Overview in Section 8). Reactogenicity diary information will be transferred to the sponsor. After review and verbal discussion of the initial reactogenicity diary entries with the participant, the investigator will

complete his/her own assessment in the relevant sections of the eCRF. Once a solicited sign or symptom from a reactogenicity diary is considered to be of severity Grade 1 or above, it will be recorded as a solicited AE.

Solicited Injection Site (Local) Adverse Events

Participants will be asked to note in the reactogenicity diary occurrences of injection site pain/tenderness, erythema and swelling at the study vaccine injection site daily for 7 days post-vaccination (day of vaccination and the subsequent 7 days). The extent (largest diameter) of any erythema and swelling should be measured (using the ruler supplied) and recorded daily. The case definitions for solicited injection site events can be found in the references ([ECDC 2020](#); [Ad26.COV2.S IB](#)).

Solicited Systemic Adverse Events

Participants will be instructed on how to record daily temperature using a thermometer provided for home use. Participants should record the temperature in the reactogenicity diary in the evening of the day of vaccination, and then daily for the next 7 days approximately at the same time each day. If more than one measurement is made on any given day, the highest temperature of that day will be used in the eCRF.

Fever is defined as endogenous elevation of body temperature $\geq 38^{\circ}$ C or $\geq 100.4^{\circ}$ F, as recorded in at least 1 measurement ([Marcy 2004](#)).

Participants will also be instructed on how to note signs and symptoms in the reactogenicity diary on a daily basis for 7 days post-vaccination (day of vaccination and the subsequent 7 days), for the following systemic events: fatigue, headache, nausea, and myalgia.

Unsolicited Adverse Events

Unsolicited AEs are all AEs for which the participant is not specifically questioned in the participant reactogenicity diary.

Medically-attended Adverse Events

MAAEs are AEs with medically-attended visits including hospital, emergency department, urgent care clinic, or other visits to or from medical personnel for any reason. New onset of chronic diseases will be collected as part of the MAAEs. Routine study visits will not be considered medically-attended visits.

For details about AESIs, refer to Section [8.3.6](#).

8.3.3. Follow-up of Adverse Events, Medically-attended Adverse Events, Adverse Events of Special Interest, and Serious Adverse Events

The investigator is obligated to perform or arrange for the conduct of supplemental measurements and evaluations as medically indicated to elucidate the nature and causality of the AE, AESI, SAE, MAAE, or PQC as fully as possible. This may include additional laboratory tests or investigations, histopathological examinations, or consultation with other health care professionals.

Adverse events, including pregnancy, will be followed by the investigator as specified in Section 10.4.

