4. STUDY DESIGN

4.1. Overall Design

This is a randomized, observer-blind, pivotal Phase 2 study in healthy adolescents from 12 to 17 years of age. The safety, reactogenicity, and immunogenicity of Ad26.COV2.S in a 1- and 2-dose (56-day interval) vaccination regimen will be evaluated. The study will descriptively compare the immune responses measured by S-ELISA (and potentially VNA) in adolescents versus the immune responses measured in young adults (18 to 25 years of age) from study VAC31518COV3001 (after administration of 1 dose of Ad26.COV2.S) or VAC31518COV3009 (after administration of 2 doses of Ad26.COV2.S) and between study groups in VAC31518COV3006. This study consists of a Dose Selection Cohort (Table 2).

Previously, this study was designed to comprise Part 1 and Part 2, wherein Part 2 included the Extension Cohort of vaccine naïve participants for evaluation of the dose level and dose regimen selected after review of the data in Part 1. Per protocol amendment 4, Part 2 will no longer be conducted

Participants will receive Ad26.COV2.S as a first dose and Ad26.COV2.S or placebo as a second dose. Ad26.COV2.S will be administered IM at 1 of up to 3 dose levels: 2.5×10^{10} vp, 1.25×10^{10} vp, or 0.625×10^{10} vp.

A target of approximately 300 adolescents seronegative for SARS-CoV-2 antibodies at baseline (as assessed by local serology finger-prick testing) will be enrolled in a 2-dose vaccination regimen

with 1 or 2 active vaccinations, with placebo administered as a second dose for those in the 1-dose regimen.

Participants in a Dose Selection Cohort will be randomly assigned in a 1:1:1:1:1:1 ratio to 1 of 6 study arms: a) to receive one active vaccination of Ad26.COV.2 (either 2.5×10^{10} vp per 0.25 mL dose volume, 1.25×10^{10} vp, or 0.625×10^{10} vp) followed by placebo at Day 57 in a 1-dose regimen (Groups 1, 2, and 3, respectively), or b) to receive 2 active vaccinations of the same dose level (either 2.5×10^{10} vp per 0.5 mL dose volume, 1.25×10^{10} vp, or 0.625×10^{10} vp) in a 2-dose (56-day interval) regimen (Groups 4, 5, and 6, respectively). Each group will contain 50 participants, of which approximately 70% need to be 12 to 15 years of age and approximately 30% need to be 16 to 17 years of age to limit unnecessary exposure in case of safety concerns (including specific pausing rules, see Section 6.8). Adolescents will be unblinded to the primary vaccination regimen at 6 months after the first vaccination.

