Participants in Groups 1-3 will be given a booster vaccination as of 6 months after the last vaccination with active vaccine (Vaccination 1). The booster dose level for all participants in Groups 1-3 will be 2.5×10^{10} vp per 0.5 mL.

Participants in Groups 4-6 will not be administered a booster vaccination, given they will receive 2 active vaccinations in the primary vaccination regimen.

As a part of the COVID-19 program safety oversight, the IDMC will review the data on an ongoing basis, in addition to two study-specific predefined IDMC analyses. A first IDMC analysis of Part 1 will be performed on safety and reactogenicity data 28 days post-dose 1. A second IDMC analysis of Part 1 will be performed on safety and reactogenicity data 28 days post-dose 2. Selected sponsor members will review group unblinded summaries of those data, as well as any available immunogenicity data up to 28 days post-dose 1 and 14 days post-dose 2. Based on the review, the sponsor will select the dose level for any future pediatric studies based on the safety and reactogenicity data (28 days after each vaccination) and any available immunogenicity data (28 days post-dose 1 for the 1-dose regimen, and 14 days post-dose 2 for the 2-dose regimen). Non-binding guidelines on dose and regimen selection will be described in the SAP. Decision making on the optimal dose and regimen may take into account safety, reactogenicity and immunogenicity data from other Ad26.COV2.S clinical studies (such as that of young adults in study VAC31518COV3001 and study VAC31518COV3009 and adolescents from study VAC31518COV2001).

The randomization will take into account having not more than 70% males or females in each age group, as evenly divided as possible over the different age groups. Stratification is by sex and age group. Screening will aim to ensure participants are seronegative for SARS-CoV-2 antibodies at baseline by utilizing the finger-prick test (by testing blood from a small puncture in the finger).

Table 2: Part 1 Vaccination Schedules (Dose Selection Cohort)

Group	N ^{a,b,c}	Vac 1	Vac 2	Vac 3 ^d
		Day 1	Day 57	Day 184
1	50	2.5×10 ¹⁰ vp (0.25 mL)	Placebo	2.5×10 ¹⁰ vp (0.5 mL)
2	50	1.25×10 ¹⁰ vp	Placebo	2.5×10 ¹⁰ vp (0.5 mL)
3	50	0.625×10 ¹⁰ vp	Placebo	2.5×10 ¹⁰ vp (0.5 mL)
4	50	2.5×10 ¹⁰ vp (0.5 mL)	2.5×10 ¹⁰ vp (0.5 mL)	
5	50	1.25×10 ¹⁰ vp	1.25×10 ¹⁰ vp	
6	50	0.625×10 ¹⁰ vp	0.625×10 ¹⁰ vp	

N = number of participants; Vac = vaccination; vp = virus particles.

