5.1.2. Study Phases

To assess study phases, in case the time of the vaccination is missing, the time will be imputed with 00:00 before applying the phase and period derivation rules. When the time of the first vaccination is missing and it occurred on the same day as the randomization, the time of vaccination will be imputed with the time of randomization.

The safety analysis results will be presented by phase/period.

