5.1.3.1. Other Follow-up Visits

The following other time intervals will be derived for safety data summary as shown in [Table 4](#).

Table 4: Other Time Intervals

Time Intervals	From	To
Up to Day 85 (only for the primary analysis)	Date and time of first vaccination	Maximum of: a) Post-dose 1 end date b) Follow-up 1 end date c) Post-dose 2 end date
Primary Vaccination Period	Date and time of first vaccination	Maximum of: a) Post-dose 1 end date b) Follow-up 1 end date c) Post-dose 2 end date d) Follow-up 2 end date e) Long term follow-up
Booster Vaccination Period	Date and time of Booster Vaccination	Maximum of: a) Post-dose 3 end date b) Booster follow-up 1 end date c) Booster long term follow-up
Entire Study	Date and time of first vaccination	Maximum of: a) Primary Vaccination Period end date b) Booster Vaccination Period end date

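### After Day 85 unsolicited AEs are collected differently in the 1-dose and 2-dose groups, so tables of all unsolicited AEs for Follow-up 2 and the whole-period intervals are not comparable

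*Protocol*

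**What the plan says.** **Collection (Protocol Section 8.3.1).** General unsolicited AEs "will be reported for each vaccination from the time of vaccination until 28 days post-vaccination". Events that begin more than 28 days after the previous study vaccination, "which are ongoing on the day of the subsequent vaccination, should be recorded as such". Several event types are collected beyond the 28 days in every group. SAEs, AESIs, AEs leading to discontinuation and AEs related to study procedures are collected to the end of participation. MAAEs are collected until 6 months after each vaccination.

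**Vaccinations (Protocol Section 4.1 and Table 2).** All six groups receive a second injection at Day 57: placebo in Groups 1-3, active vaccine in Groups 4-6. Only Groups 1-3 have a third, the booster at target Day 184.

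**Analysis (SAP).** Section 5.1.2: "The safety analysis results will be presented by phase/period". Table 3 defines Follow-up 1 and Follow-up 2 phases next to the post-dose periods. Section 5.1.3.1 adds Table 4: "The following other time intervals will be derived for safety data summary", among them Up to Day 85 (primary analysis only), Primary Vaccination Period and Entire Study. Section 5.7.1.4 allocates AEs by start date. Section 5.7.1.3 lists the unsolicited AE tables (all, most frequent, grade 3 or more, related, SAE) without saying which phases they cover. Section 5.7.1.5 counts a participant with no reported event as a participant without an event.

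**The concern.** An AE table compares groups fairly only if the groups had the same chance of having an event recorded. Here that chance depends on whether a further vaccination follows. After Day 85 this separates the 1-dose from the 2-dose regimen, which is one of the main contrasts of the trial.

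A minor, unattended AE that starts on Day 170 and is still present on Day 184 enters the database for a participant in Group 2 and is counted in Follow-up 2. The same event in Group 5 is never collected and enters the table as no event. Nothing in the SAP tells the reader of a Follow-up 2 or Entire Study table that the groups were observed differently.

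**Working it through.** There is no plan figure to reproduce. The check sets the collection windows against the SAP phases on target days and then gauges the size under stated assumptions.

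**1. Calendar.** Second injection: 1 + 56 = Day 57. Post-dose 1 ends on Day 29 and Post-dose 2 on Day 57 + 28 = 85. Booster: 1 + 183 = Day 184. Last visit in Groups 4-6: 57 + 183 = Day 240. These agree with the Schedule of Activities.

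**2. Intervals.**

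| Interval | Groups 1-3 | Groups 4-6 |
|---|---|---|
| Follow-up 1 | Days 30-56 (27 days), closed by an injection | Days 30-56 (27 days), closed by an injection |
| Up to Day 85 | two 28-day windows, rule applies at Day 57 | the same |
| Follow-up 2 | Days 86-183 (184 - 86 = 98 days), closed by the booster | Days 86-239 (240 - 86 = 154 days), no injection after it |
| Primary Vaccination Period | two windows, rule applies at Days 57 and 184 | two windows, rule applies at Day 57 only |
| Entire Study | three windows | two windows |

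Collection matches between the sets through Day 85 and differs afterwards.

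**3. Size of the carry-over (assumptions, not document figures).** Let r be the onset rate of AEs that only this rule would record, D their mean duration and g the gap in days. The probability that at least one such AE is ongoing at the next vaccination is

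P = 1 - exp{-r × D × (1 - exp(-g/D))}.

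Take r = 0.5 to 2 per person-year, D = 5 to 20 days, and 150 participants per set of groups, all vaccinated:

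- Day 57 (g = 27): about 1.0 to 11.7 participants in each set.
- Day 184 (g = 98): about 1.0 (r = 0.5, D = 5) to 15.4 (r = 2, D = 20) in Groups 1-3. With r = 1 and D = 10 the figure is 4.1.
- After Day 85 in Groups 4-6: 0.

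Such events arising over the 98 days in Groups 1-3 number 150 × r × 98/365.25, or about 20 to 80. Even there the rule captures only about D/98 of them (5/98 = 5% to 20/98 = 20%).

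**4. Direction.** Now let r be the onset rate per day of all unsolicited AEs and f the share that is medically attended. MAAEs are collected throughout Follow-up 2 in both sets. Expected recorded events per person in Follow-up 2 are approximately:

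- Groups 1-3: r × {98f + (1 - f)D}
- Groups 4-6: r × 154f

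They are equal when (1 - f)D = 56f, that is f = D/(56 + D), whatever r is:

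- D = 5: 5/61 = 8%
- D = 10: 10/66 = 15%
- D = 20: 20/76 = 26%

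Below that share Groups 1-3 show more events; above it Groups 4-6 do. The documents do not give f or D.

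**The case against.** **Little is lost.** Serious, special-interest, medically attended, procedure-related and discontinuation AEs are still collected in Groups 4-6. Only the remaining, mostly minor, events are affected. Long-lasting events are the ones most likely to lead to a medical visit, and an acute illness or fever can postpone the booster, so some events will have resolved by the actual booster day. This stands and keeps the effect small. It does not make the tables comparable.

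**The endpoints are 28-day endpoints.** The primary unsolicited AE endpoint covers 28 days after doses 1 and 2, and the secondary one 28 days after the booster. The safety analysis is descriptive, and the choice of tables by phase may be settled in the Data Presentation Specifications, which are not available here. This also stands in part. However, the SAP as written calls for presentation by phase and over the Table 4 intervals and sets no limit on the unsolicited AE tables.

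**Stronger readings the documents do not support.** A reader might infer any of the following:

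- *Groups 4-6 never benefit from the rule.* They do at Day 57, exactly as Groups 1-3 do, so Follow-up 1 and Up to Day 85 are symmetric.
- *The 1-dose groups will show an excess.* This ignores the 56 extra days of MAAE collection in Groups 4-6 during Follow-up 2; step 4 of the working shows that the sign can go either way.
- *Full collection of 58 of 183 days (32%) against 58 of 240 (24%) measures the bias.* Both sets have the same 58 fully collected days in the primary period, and the tables report participants, not events per unit time.
- *The fall from Post-dose 1 to Follow-up 1 is a between-group bias.* It follows from the 28-day window and is the same in all six groups.

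**Conclusion.** The point holds for the period after Day 85. Tables of all unsolicited AEs for Follow-up 2, Primary Vaccination Period and Entire Study would be incomplete and not comparable between the regimens, for three reasons:

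- The carry-over rule works only in boosted Groups 1-3 participants.
- Follow-up 2 lasts about 98 days in Groups 1-3 and 154 in Groups 4-6.
- Entire Study has three fully collected windows in Groups 1-3 and two in Groups 4-6.

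The asymmetry follows from the documents alone. Its size does not: the range of about 1 to 15 added participants per 150 (0.7% to 10%) rests on assumed rates and durations and on every participant being boosted. Heavier assumptions raise it. At 0.4 AEs per month and 20 days, 1 - exp(-0.4/30 × 20) = 23%, but that rate has no source in the documents. The net direction is unknown.

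The primary 28-day unsolicited AE endpoint is unaffected. So is dose selection, which uses data up to 28 days after dose 2. This is a reporting weakness that should be corrected, not a threat to the primary conclusions.

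**What to change.** In SAP Section 5.7.1.3:

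1. Present the unsolicited AE tables (all, most frequent, grade 3 or more, related) for Post-dose 1, Post-dose 2 and Post-booster only. This matches the 28-day endpoints.
2. For the follow-up phases and the Table 4 intervals, tabulate only the types collected continuously: SAEs, AESIs, MAAEs within their 6-month window, AEs leading to discontinuation, and procedure-related AEs. State the length of each interval by group, because 98 against 154 days still matters for these types.
3. Show AEs recorded only because they were ongoing at the next vaccination in a separate flagged row or table, plus a listing. A listing alone would not do, since Protocol Section 9.4.2 keeps all reported AEs in the analysis.

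The cost is a small change to SAP wording and table layout. No new data are needed and none are dropped.
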